NCT04318444

IRB Protocol
AAAS 9676
April 30, 2020
Modification 7

Hydroxychloroquine Post Exposure Prophylaxis (PEP) for High-Risk Contacts of COVID-19 Patients: A
NYC Community-Based Randomized Clinical Trial

Investigators:

[name], MPH (PI)
[name], MPH
[name] [name] (Statistician)
[name] [name], MS
[name]
[name], MPH

1. Study Purpose and Rationale

COVID-19 is a massive threat to public health worldwide. Current estimates suggest that the novel coronavirus (SARS-CoV-2) is both highly contagious (estimated reproductive rate, 2-3) and five to fifty-fold more lethal than seasonal influenza (estimated mortality rate, 0.5-5%). Interventions to decrease the incidence and severity of COVID-19 are emergently needed.

Hydroxychloroquine (brand name, Plaquenil), an inexpensive anti-malarial medication with immunomodulatory effects (1-4), is a promising therapy for COVID-19. Chloroquine, a related compound with a less favorable toxicity profile, has shown benefit in clinical studies conducted in approximately one-hundred SARS-CoV-2 infected patients (1, 2). In vitro, hydroxychloroquine has been recently shown to have greater efficacy against SARS-CoV-2 versus chloroquine (5). Although the molecular mechanisms of action are incompletely understood, previous studies suggest that hydroxychloroquine may inhibit coronaviruses by changing cell surface pH, inhibiting the fusion of the virus to the cell membrane, and by inhibiting nucleic acid replication, glycosylation of viral proteins, virus assembly, new virus particle transport, and virus release (6).

The safety profile of hydroxychloroquine has been well-established over decades of regular use by patients with autoimmune disease. Indeed, hydroxychloroquine is on the World Health Organization (WHO) list of essential medications, highlighting it as one of the safest and most effective medications on the market. The major toxicity with short term use is QT prolongation, which may increase risk of arrhythmia. Other known toxicities include retinopathy, which is mainly observed at high daily doses (>5mg/kg/day), and hematologic abnormalities (agranulocytosis, thrombocytopenia).

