Study drug: the intervention will be a 5-day course of hydroxychloroquine sulfate (brand name, Plaquenil). Each participant will receive 12 tablets of hydroxychloroquine sulfate 200mg. They will be instructed to take two tablets (400mg) twice daily on day 1; for days 2-5, they will be instructed to take one tablet (200mg) twice daily. The rationale for this dosing regimen is as follows. A loading dose is important to efficacy, but loading doses >800mg/24 hours are expected to have a disadvantageous risk/benefit profile. The dose on the subsequent 4 days

(400mg/day) is within the standard long-term daily dosing range for autoimmune diseases. For comparison, other current trials of hPEP propose the following regimens:

- NCT04304053: 800mg on day 1, and 400mg on days 2, 3, 4. We believe that an additional day of therapy will be associated with minimal excess risk and the median incubation of CoV-SARS-2 is 5 days, suggesting that 5 days of prophylaxis may be superior to 4 days.
- NCT04308668: 800 mg orally once, followed in 6 to 8 hours by 600 mg, then 600mg once a day for 6 consecutive days. We believe that the loading dose and the follow-up doses are excessively high. Together with an extended (7-day) course of treatment, we believe that this regimen carries higher risk of adverse effects without clear benefit and with lower likelihood of regimen adherence.

Participants randomized to the placebo will receive an identical container of 12 placebo pills, with the same instructions for administration.

Follow up

Participant self-monitoring: participants will be asked to check and record their temperatures at home in the morning and in the evening. They will be instructed to contact the study if they develop a temperature >38 C, and/or if they develop cough or shortness of breath.

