- i. Hydroxychloroquine dose pack: 5-day course of hydroxychloroquine sulfate (brand name, Plaquenil). Each participant will receive 12 tablets of hydroxychloroquine sulfate 200mg. They will be instructed to take two tablets (400mg) twice daily on day 1; for days 2-5, they will be instructed to take one table (200mg) twice daily.
- ii. Placebo daily: Participants randomized to the placebo will receive an identical container of 12 placebo pills, with the same instructions for

administration.

c. Confidentiality of Study Data: The consent form signed by the participant will provide written assurance that all individual data collected in the study will be kept confidential to the extent provided by the Privacy Act of 1974. Any personal identifiers will be maintained on limited-access, secure servers and never put on endpoint devices so that confidential data are not released. Participants will be informed that: (1) the only people who will know that they are research participants are members of the research team and, if appropriate, their physicians or health care providers; (2) no individual identifying information about them will be disclosed to others, except if required by law; and (3) when the results of the study are published or discussed in conferences, no information will be included that would reveal their identity. Coded research data will be stored on password-protected, secure servers hosted by the Division of General Medicine and certified by CUIMC IT the CUIMC Radiology PACS, and in locked filing cabinets in General Medicine, and potentially on endpoint devices that will, in all cases, be encrypted. Identifiable data will be stored in the General Medicine Server described above and in locked filing cabinets in separately partitioned drives/cabinets. The linking file will be similarly protected with limited access.

d. Potential Risks:

- i. Retinopathy: Hydroxychloroquine treatment has been associated with development of retinopathy, particularly at doses >5mg/kg/day. We will exclude participants <40 kg for whom the study dose might exceed this threshold. We will also exclude persons with established retinopathy from the study.
- ii. Hematologic abnormalities: we will exclude individuals with known G6PD deficiency or hematologic malignancy.
- iii. Allergy: we will exclude participants with known sensitivity to hydroxychloroquine.
- iv. Arrhythmia: we will exclude individuals with known arrhythmia or use of anti-arrhythmic medications.

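### The 40 kg exclusion in section 3.d.i does not follow from its 5 mg/kg/day threshold, and section 3.d and the section 2 exclusion list disagree on weight and arrhythmia

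*Combined protocol and SAP*

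**What the plan says.** All references are to the combined protocol and SAP.

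- **Threshold.** Section 3.d.i associates hydroxychloroquine with retinopathy, "particularly at doses >5mg/kg/day". Section 1 gives the same figure and also ties it to the daily dose.
- **Weight exclusion.** Section 3.d.i continues: "We will exclude participants <40 kg for whom the study dose might exceed this threshold".
- **Regimen.** Section 2, Study drug, sets the first day's dose: "They will be instructed to take two tablets (400mg) twice daily on day 1". The remaining four days are at half that dose, a single 200 mg tablet morning and evening. Section 3.b repeats this. The same part of section 2 defends the 400 mg/day on days 2-5 as a dose that "is within the standard long-term daily dosing range for autoimmune diseases", and defends day 1 as a loading dose.
- **Arrhythmia exclusion.** Section 3.d.iv: "we will exclude individuals with known arrhythmia or use of anti-arrhythmic medications".
- **Exclusion list.** Section 2, Exclusion criteria, runs from a to k. No item concerns body weight. Item k.iii covers a history of ventricular arrhythmia, and item k.iv covers current use of the QT-prolonging drugs in Table 1.
- **Main short-term risk.** Section 1: "The major toxicity with short term use is QT prolongation, which may increase risk of arrhythmia".

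**The concern.** There are two separate faults.

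The first is arithmetic. The weight sentence presents 40 kg as the point below which the dose could pass 5 mg/kg/day. Someone assessing risk from section 3.d.i would conclude that participants of 40 kg or more stay at or under the threshold. Most of the plausible adult weight range lies above 40 kg and below 160 kg, where the threshold is passed on at least one day.

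The second is a conflict over eligibility. Section 3.d states two exclusions that the list in section 2 either lacks (weight) or states more narrowly (arrhythmia). A person with a known non-ventricular arrhythmia who takes no Table 1 drug is excluded by section 3.d.iv and eligible under section 2. A person under 40 kg is excluded by section 3.d.i and eligible under section 2. No text says which section governs. The arrhythmia conflict matters more, because the protocol names QT prolongation as the main short-term toxicity and because resolving it can change who is dosed.

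**Working it through.** **Part 1: the weight limit**

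Inputs: threshold 5 mg/kg/day (sections 1 and 3.d.i); 200 mg tablets, 12 per participant, two twice daily on day 1 and one twice daily on days 2-5 (sections 2 and 3.b).

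Formula: weight below which the threshold is exceeded = daily dose (mg/day) ÷ 5 mg/kg/day.

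1. Trying to reproduce 40 kg: 40 × 5 = 200 mg/day. No day of the regimen uses that dose.
2. Day 1: 2 × 200 × 2 = 800 mg; 800 ÷ 5 = **160 kg**.
3. Days 2-5: 1 × 200 × 2 = 400 mg/day; 400 ÷ 5 = **80 kg**.
4. Mean over the 5 days: 12 × 200 = 2400 mg (= 800 + 4 × 400); 2400 ÷ 5 = 480 mg/day; 480 ÷ 5 = **96 kg**.
5. Mean over the follow-up periods: 7 days, 2400 ÷ 7 ÷ 5 = 68.6 kg; 14 days, 2400 ÷ 14 ÷ 5 = 34.3 kg; 30 days, 2400 ÷ 30 ÷ 5 = 16 kg. None gives 40.
6. One 200 mg tablet used in place of the daily dose: 200 ÷ 5 = 40 kg. This suggests that a single dose was taken for the daily dose, but that origin is an inference.

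Dose per kg at selected weights:

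| Weight (kg) | Day 1, 800 ÷ weight (mg/kg) | Days 2-5, 400 ÷ weight (mg/kg/day) |
|---|---|---|
| 40 | 20.0 | 10.0 |
| 60 | 13.3 | 6.7 |
| 80 | 10.0 | 5.0 |
| 100 | 8.0 | 4.0 |
| 160 | 5.0 | 2.5 |

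A participant of exactly 40 kg, whom the sentence admits, takes 2 times the threshold on days 2-5 (10 ÷ 5) and 4 times on day 1 (20 ÷ 5). From 40 kg to just under 80 kg the threshold is exceeded on all five days. From 80 kg to just under 160 kg it is exceeded on day 1 only.

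**Part 2: section 3.d against the exclusion list**

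| Exclusion stated in section 3.d | Item in the section 2 list |
|---|---|
| Retinopathy (3.d.i) | i |
| Body weight under 40 kg (3.d.i) | none |
| G6PD deficiency, hematologic malignancy (3.d.ii) | j, k.i |
| Sensitivity to the drug (3.d.iii) | f |
| Any known arrhythmia (3.d.iv) | k.iii, ventricular only |
| Anti-arrhythmic drugs (3.d.iv) | k.iv with Table 1 |

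The last row is largely covered: Table 1 opens with antiarrhythmics as a class, names several, and is not worded as exhaustive. It is also wider than 3.d.iv, since it adds other drug classes. The two mismatches that remain are weight and non-ventricular arrhythmia.

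On screening, section 2 (Screening) and section 3.a.i say that the interview covers the inclusion and exclusion criteria. They do not say whether this means the list alone or the list together with section 3.d. The summary of the first-call forms in section 3.a.i does not mention weight.

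**The case against.** The strongest reply has four parts.

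- **Section 3.d may be shorthand.** Its other exclusions restate list items briefly, so 3.d.iv could be a loose reference to k.iii and k.iv. This is a possible reading of the arrhythmia sentence. It cannot account for a weight exclusion with no counterpart in the list, or for the wrong limit. As written, the two arrhythmia rules still admit different people.
- **The list already protects participants before dosing.** It excludes QT-prolonging drugs, ventricular arrhythmia, stage 4-5 kidney disease or dialysis, and prior retinopathy. This stands, and it lowers the risk attached to the mismatch.
- **The weight error has little clinical consequence.** Section 1 places retinopathy among the other toxicities, not as the main short-term one, and section 2 justifies the dose on separate grounds. This also stands. A reader might infer that the wrong limit exposes participants to retinal harm, or that it ought to be raised to 80 or 160 kg. The documents support neither: they do not say that 5 mg/kg/day is a safety limit for a 5-day course.
- **The screening forms are not shown.** A reader might infer that the weight and wider arrhythmia exclusions would not be applied in practice. That cannot be established. Section 3.d is itself protocol text, and the screening interview could cover it. What can be shown is that the text leaves the governing rule unclear.

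**Conclusion.** Both parts hold, and the text should be corrected. The 40 kg figure is wrong as a derivation from 5 mg/kg/day: on the stated regimen the threshold is exceeded below 160 kg on day 1 and below 80 kg on days 2-5. The exclusions in section 3.d and in the section 2 list conflict on weight and on non-ventricular arrhythmia, and the protocol does not say which prevails.

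The arithmetic assumes dosing as directed and reads the threshold as a daily dose, as sections 1 and 3.d.i both express it. The documents give no weight distribution and no prevalence of arrhythmia, so the share of participants affected cannot be estimated. A reader might also take the lack of any described ECG before dosing as part of this point. That is a separate design question and does not follow from the mismatch. Sample size, power and the planned analyses are unaffected.

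**What to change.** 1. Put the section 3.d.iv rule (any known arrhythmia, or use of anti-arrhythmic drugs) in the section 2 exclusion list, and keep item k.iv and Table 1. This makes the protection already stated in section 3.d part of the list used to define eligibility. The eligible pool becomes somewhat smaller, by an amount the documents do not allow to be estimated.
2. Correct section 3.d.i to say that the dose exceeds 5 mg/kg/day below 160 kg on day 1 and below 80 kg on days 2-5. State that the dose is justified by the short course and, for days 2-5, by the standard dosing range already cited in section 2.
3. Decide on the 40 kg exclusion. Either delete it, since the stated derivation fails and a short course argues against needing it; or keep it as a general low-weight safeguard, described as such, and add it to the section 2 list with a self-reported weight item on the screening questionnaire.

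The cost is a wording amendment and, if the weight rule is kept, one extra screening field. No statistical section needs to change.

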We propose a single-center, double-blinded, placebo-controlled, randomized, Phase 2-3 clinical trial to test if hydroxychloroquine post exposure prophylaxis (hPEP) reduces the symptomatic secondary attack rate of COVID-19 among close contacts of known or suspected COVID-19 patients identified at the largest academic medical center in NYC and surrounding metropolitan area.

Setting: The study will be conducted in NYC, where the COVID-19 epidemic is rapidly accelerating. In order to optimize efficiency, the study will be initiated at the NYP/CUIMC campus in Washington Heights, with plans to expand across other NYP campuses if/as conditions allow. As this is a community-based study, where interaction is facilitated remotely, we wish to include the tri-state area as our immediate scope due to the patient demographic majority residing in this area.

Population: Currently asymptomatic adults (≥ 18 years old) meeting the following inclusion and exclusion criteria:

a. Inclusion criteria:

- a. Household contact of index case: currently residing in the same household as an index case:
 - i. Index case definition: individual evaluated at outpatient, emergency department (ED), or inpatient services who (1) tests positive for COVID-19, or (2) are defined as suspected cases, or persons under investigations (PUI), by the treating physician.
- b. Willing to take study drug as directed for 5 days.

b. Exclusion criteria:

- a. Age < 18 years old
- b. Suspected or confirmed current COVID-19, defined as: (1) temperature > 38 Celsius; (2) cough; (3) shortness of breath; (4) sore throat; or, if available (not required), (5) positive confirmatory testing for COVID-19
- c. Suspected or confirmed convalescent COVID-19, defined as any of the above symptoms within the prior 4 weeks.
- d. Inability to take medications orally
- e. Inability to provide written consent or eConsent
- f. Known sensitivity/allergy to hydroxychloroquine

- g. Current use of hydroxychloroquine for another indication
- h. Pregnancy
- i. Prior diagnosis of retinopathy
- j. Prior diagnosis of G6PD deficiency
- k. Major comorbidities increasing risk of study drug:
 - i. Hematologic malignancy
 - ii. Advanced (stage 4-5) chronic kidney disease or dialysis therapy
 - iii. Known history of ventricular arrhythmias
 - iv. Current use of drugs that prolong the QT interval (Table 1)

Table 1. Drugs that prolong QT, and for which current use will be an exclusion criterion for participation

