Daily telephone or email follow-up: research personnel will contact participants by phone on a daily basis for 7 days post-randomization, and at 14 (+/- 3) and 30 days (+/- 3). They will conduct a structured interview to ascertain potential symptoms of COVID-19 (the primary outcome), adherence to and potential adverse effects of the study drug, and extent of ongoing exposure to the index case. Alternatively, if preferred by the participant, the participant will be able to submit answers to the daily symptomatic questionnaire via secure web-based questionnaire to support remote administration and immediate data capture. Participants with symptoms or signs of COVID-19 will be referred to the study physician, who will contact the participant and determine if he/she meets PUI criteria. The study physician will refer PUIs for confirmatory COVID-19 testing at NYP/CUIMC/WCMC.

Psychosocial Questionnaire at Day7: Resources for mental health and wellness are provided at the end of the psychosocial questionnaire for all participants, as well as instructions for seeking medical attention if participants experience significant distress or feel unsafe.

Participants who score in the severe or extremely severe range on the depression subscale, express passive or active suicidal ideation, or express thoughts of self-harm will be informed of mental health support hotlines, advised to seek care from a mental health professional, and encouraged to contact emergency services if they feel unsafe. For such participants who respond to the questionnaire online or by paper, an attempt will be made to contact them at the time the questionnaire is viewed to provide the information above.

Active surveillance of healthcare utilization: the research personnel will monitor study participants to determine if any participants present to the outpatient clinic or to the ED, and/or if they require hospitalization.

Extended follow-up of symptomatic participants: participants who develop COVID-19 symptoms will continue to be followed-up by daily telephone calls until 3 days following resolution of

symptoms in order to measure the duration of symptom (secondary endpoint).

Statistics

We plan a phase 2 study at NYP/CUIMC/WCMC, with the phase 2 as an internal pilot for a potential phase 3 study, which would be conducted across all NYP sites.

Population: Household contacts of COVID-19 cases with high-risk COVID-19 exposures

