The primary analysis will be comparing the rates of symptomatic, lab-confirmed COVID-19 in all randomized participants using one-sided Fisher's exact test. Intent-to-treat analysis will be used. Secondary endpoints include duration of COVID-19 symptoms without confirmatory test, hospitalization for COVID-19, requiring mechanical ventilation, and mortality. Statistical analysis of the secondary endpoints will be intent-to-treat, using Mann-Whitney test for numerical outcomes and Fisher's test for categorical outcomes. Adverse events and serious adverse events will be compared using Fisher's exact test. Interim analysis will be performed to monitor for futility using a Bayesian criterion. Specifically, an early stopping consideration will be invoked if it is unlikely that poor outcome of hPEP is lower than that of placebo; i.e., its posterior probability is smaller than alpha. The value of alpha will be determined before the first interim analysis.

Go and no-go decision and power consideration

We will plan to move forward to the phase 3 trial if at the end of the pilot phase, the primary analysis has a one-sided p-value less than 0.10. Assuming the placebo rate of COVID-19 outcome is 10.5%, the proposed sample size in the internal pilot will result in an 80% probability of moving forward if the study drug reduces risk by 30% (i.e., from 10.5% to 7.3%).

In addition, the pilot data will be used to re-estimate the sample size in the phase 3 trial, and will be used in the final analysis using adjusted analysis using weighted statistics so as to preserve the overall type I error. Details of sample size re-estimation will be determined before the pilot trial data is unblinded.

3. Study Procedures

a. Procedures

- i. Questionnaires: questionnaires will be performed by telephone by trained research assistants or via web-based questionnaire to support remote administration and immediate data capture.
 1. Screening questionnaire (first call): inclusion and exclusion criteria
 2. Medical history questionnaire (first call): additional questions regarding medications used, number of persons in household
 3. Follow-up questionnaires
 - a. Symptoms (respiratory, non-respiratory)
 - b. Trial medicine adherence
 - c. Psychosocial Behavior (Day7 only)
- ii. Active surveillance for health care utilization and COVID-19 testing at NYP/CUIMC
 1. Participants will be referred for clinical COVID-19 testing if deemed PUI by the study investigator(s)

b. Study Drugs

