e. Protections Against Risks:

- i. In addition to strict exclusion criteria, we will monitor participants for signs/symptoms of potential adverse effects of the study drug by daily follow-up for 7 days. On Day 7, a specific interview concerning acute side-effects of the study medication will be conducted. If any adverse drug effects are suspected based upon symptomatic report, the study physician will determine whether the symptoms are attributable to the study drug. Beyond the two-week period of initial follow-up, we will encourage all participants to reach out to the study coordinator for palpitations, dyspnea on exertion, or visual disturbances occurring up to 30 days after completion of participation. Serious adverse events (SAEs) will be recorded for the full duration of subject participation, however only adverse events of special interest will be recorded upon the Day 7 acute side-effect interview.
- ii. To mitigate risks of COVID-19 among participants, all participants will receive counseling and information regarding current CDC guidelines for exposed household contacts of COVID-19 patients (e.g., decontamination of surfaces, avoidance of unprotected contacts with the index case).

f. Potential Benefits: if the study drug is effective, those randomized to the study drug may benefit from improved COVID-19 outcomes. If benefit is demonstrated, participants randomized to the control arm will have the opportunity to obtain the study drug after study completion. The societal benefits are potentially large.

g. Alternatives: non-participation. Data Safety and Monitoring Plan: A local Data and Safety Monitoring Committee (DSMC) has been established, with [name] (rheumatology) as Chairman of the committee. In addition, the committee will consist of two other members, a pharmacist (TBD) and a statistician ([name]). The DSMC will meet to review all safety data from the patients after the first 100 randomized patients completing their 2-week follow-up, and every 400 randomized patients thereafter. The unblinded statistician will prepare the data for DSMC's review. Each meeting will consist of an open session that includes the study investigators, and a closed session with only the unblinded statistician and the DSMC members.

References

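### The request to call the study about palpitations or visual disturbances starts only after two weeks, leaving 6 or 7 of days 8-14 with neither that prompt nor a routine contact

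*Combined protocol and SAP*

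**What the plan says.** Four parts of the combined protocol and SAP bear on this.

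- **Scheduled contacts** (section 2, Follow up, daily telephone or email follow-up). Staff will "contact participants by phone on a daily basis for 7 days post-randomization, and at 14 (+/- 3) and 30 days (+/- 3"). The interview covers COVID-19 symptoms, adherence and possible adverse effects. A web questionnaire may replace the call.
- **Standing instruction to participants** (section 2, Participant self-monitoring). "They will be instructed to contact the study if they develop a temperature >38 C, and/or if they develop cough or shortness of breath". No start or end day is given.
- **Drug-safety instruction** (section 3.e, Protections Against Risks). "Beyond the two-week period of initial follow-up, we will encourage all participants to reach out to the study coordinator for palpitations"; the sentence goes on to exertional dyspnea and visual disturbances, and runs until 30 days past the end of participation. The same item provides for adverse-effect monitoring through the seven daily contacts, and adds: "On Day 7, a specific interview concerning acute side-effects of the study medication will be conducted".
- **Other cover.** For those who fall ill, "participants who develop COVID-19 symptoms will continue to be followed-up by daily telephone calls until 3 days following resolution" of symptoms. For everyone, "the research personnel will monitor study participants to determine if any participants present to the outpatient clinic or to the ED", and whether they are admitted. SAEs are recorded throughout participation.

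**The concern.** The rationale in section 1 names QT prolongation, with possible arrhythmia, as the main short-term toxicity of the drug, and section 3.d lists both arrhythmia and retinopathy as risks. Section 3.e treats palpitations and visual changes as worth a call even weeks after the last tablet. If so, they are at least as worth a call in the second week, which is nearer to dosing. Yet the instruction is dated to begin when that week is over, and no reason is given.

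The available text describes screening by structured interview and largely remote follow-up, and it mentions no ECG. A participant's own report is therefore a main route by which a rhythm symptom reaches the study physician. At stake is how promptly such a report arrives. Nothing here affects the primary endpoint, the analysis or the scheduled safety assessments.

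**Working it through.** The plan states no length for this gap, so there is no figure of its own to reproduce. The check is a count of days.

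**Inputs**
- Days are counted from randomization. Daily contacts fall on days 1-7 (section 2).
- The two-week contact falls on day *d*, with *d* from 11 to 17 (14 +/- 3, section 2).
- The drug-safety prompt is in force from day 15. This is an assumption: it takes day 14 as the last day of the two-week period in section 3.e.
- The participant has no COVID-19 symptoms, so daily calls do not continue.

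**Which symptoms lack an earlier prompt.** Section 3.e names three. Exertional dyspnea largely overlaps the shortness of breath in the self-monitoring instruction. Palpitations and visual disturbances do not appear there. So two of the three have no earlier prompt in the available text.

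**Count.** Days 8-14 are 14 - 8 + 1 = 7 days. One of them is covered if the contact falls on or before day 14:

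uncovered days = 7 - 1 = 6 if *d* is 11 to 14; 7 - 0 = 7 if *d* is 15 to 17.

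| Two-week contact on day | Days with neither contact nor prompt | Total |
|---|---|---|
| 11 | 8-10, 12-14 | 6 |
| 12 | 8-11, 13-14 | 6 |
| 13 | 8-12, 14 | 6 |
| 14 (nominal) | 8-13 | 6 |
| 15, 16 or 17 | 8-14 | 7 |

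An early contact does not shorten the total. It splits it, because the days between the contact and day 15 again have neither. The first unbroken run alone is min(*d*, 15) - 8, that is 3 days for *d* = 11, 6 for *d* = 14 and 7 for *d* = 15 to 17.

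**Sensitivity to the start day.** If the prompt is taken to begin on day 14, only days 8-13 (6 days) are at issue. The total is then 5 for *d* = 11 to 13 and 6 for *d* = 14 to 17. At the nominal schedule the answer is 6 either way.

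**Where dosing falls.** A 5-day course begun on day *s* ends on day *s* + 4. A start by day 3 ends by day 7, inside the daily contacts; a start on day 4 would end on day 8. Section 2 allows home delivery and gives no delivery time, so the start day is unknown. With prompt dosing, the gap lies wholly after the course.

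The documents give no rate for these symptoms after dosing, so no event count is estimated.

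**The case against.** The strongest reply is that little is left uncovered. Adverse effects are asked about daily through day 7, with a dedicated interview on that day, and the same structured interview is due again at days 14 and 30. Visits to clinic or ED, and admissions, are monitored, and SAEs are recorded throughout. Known ventricular arrhythmia, listed QT-prolonging drugs and prior retinopathy are exclusions, and section 1 says retinopathy is seen mainly at high daily doses. Participants have been in daily touch with the study and can call unprompted. An instruction on what to report would ordinarily sit in the consent form, whose pages were removed. Finally, *Beyond* could loosely mean *in addition to*.

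Most of this stands, and it limits the harm to a late report. It does not remove the gap in section 3.e as written. *After* is the natural sense of *Beyond* there, and the other provisions rest on a visit, an SAE or the next scheduled contact, not on a prompt to call.

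A reader might infer more than the documents support:

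- **That safety during dosing is neglected.** It is not: daily contacts ask about adverse effects for the first week.
- **That participants are never told earlier.** This cannot be established without the consent pages.
- **That care outside the center would be missed**, because section 3.a lists "Active surveillance for health care utilization and COVID-19 testing at NYP/CUIMC" while the Setting paragraph says "we wish to include the tri-state area as our immediate scope". The site phrase may attach to testing only, and the fuller description of surveillance in section 2 carries no site limit.
- **That SAEs reported after participation would be lost.** Section 3.e states recording for the period of participation, but does not bar recording one volunteered later.

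**Conclusion.** The point holds as a minor, inexpensive safety improvement. For a participant free of COVID-19 symptoms, section 3.e as written leaves 6 of days 8-14 (contact on days 11-14), or all 7 (contact on days 15-17), with neither a routine contact nor a prompt naming palpitations or visual disturbances.

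This rests on reading *Beyond* as *after*, on a prompt start at day 15, and on the available text alone. The effect is a possible delay in hearing of a symptom for which the participant neither seeks care nor calls; its frequency cannot be estimated from the documents.

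**What to change.** In section 3.e, replace the opening time phrase so that the existing instruction applies from the first dose through the 30 days after completion already stated, and give it to participants with the study drug. For example: *From first dose until 30 days after participation ends, participants are asked to call the study coordinator about palpitations, exertional dyspnea or visual disturbances.* Tying it to first dose also removes any dependence on when the drug arrives. Fainting could be added to the list as an option, since arrhythmia is the named acute risk. If the participant materials already carry an earlier instruction, align section 3.e with them.

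The cost is one sentence in the protocol, one line supplied with the drug, and a few more inbound calls for the study physician to assess. No visit, test or scheduled call is added.
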